### ***Outcome measures***

During the 12-week outpatient period, participants will be interviewed for safety and efficacy endpoints and undergo a remote drug screen. Remote interviews reduce risk of COVID-19 exposure for the participant and research assistant, and decrease transportation barriers (increased feasibility). Each week, the research assistant hosts a live video call with the participant, and conducts a timeline follow-back (TLFB) review of opioid, MOUD, stimulant, sedative, cannabis and alcohol use for each of the prior 7 days. At discharge from the inpatient facility, each participant will be given 12 kits (plus

one spare) of the Premier Biotech OralTox OT-80605, an FDA 510(K) cleared 6-panel rapid oral fluid drug screen. Each test covers amphetamines and methamphetamine (positive cutoffs = 50 ng/ml), opioids and THC (positive cutoffs = 40 ng/ml), oxycodone and cocaine (positive cutoffs = 20 ng/ml). Each individually packaged test is sealed in foil and is marked with a lot number and expiration date. Each individual test contains a QR code that encodes a unique identification number that will be used to validate authenticity and uniqueness of the screen. The participant receives printed and verbal instructions for use from the research assistant, is observed during each test, and test results with authenticating QR code are captured as an image file by the research assistant and saved for validation. In order to conduct this FDA-qualifying study during the COVID-19 pandemic, remote test methods were evaluated for use during the outpatient phase. When this study began, FDA had only approved a limited selection of oral fluid rapid tests for use in research. The authors selected TLFB self-report as the primary source for data, supplemented by such relevant oral fluid tests as were FDA approved.

The primary efficacy endpoint is each participant's overall percentage of weekly abstinence from illicit opioid use without use of MOUD. This is defined as the percentage of each participant's negative oral fluid samples and self-reports of illicit opioid, methadone, buprenorphine, and naltrexone use per week throughout the 12-week outpatient study period. The rationale for choosing this endpoint is to perform a rigorous test of the isolated efficacy of NET, with the safety net of allowing (and measuring) participants' use of MOUDs.

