During a given week, oral fluid samples and self/pharmacy reports that both indicate no illicit opioid, methadone, buprenorphine, or naltrexone use will be considered "opioid-abstinence without MOUD". Cumulative distribution function, time (days) to first use of illicit opioids, time (days) to first use of MOUD, and duration (weeks) of continuous abstinence without MOUD will be evaluated as supportive outcomes. Response profiles for each treatment arm are based on each participant's individual rates of weekly illicit opioid or MOUD use, including negative oral fluid results and daily

self (TLFB) of illicit opioid or MOUD use/non-use. **Table 1** presents explanatory cases of the primary efficacy endpoint measurement. The null hypothesis is that “opioid abstinence without MOUD” will not significantly differ between active and sham groups, whereas the alternative hypothesis is that “opioid abstinence without MOUD” will be superior in the active (relative to sham) treatment arm.

The secondary efficacy endpoint is each participant’s percentage of non-opioid drug-free weeks during the 12-week outpatient period. Non-opioids assessed include cocaine, sedatives, and stimulants. Use of alcohol and cannabis will be measured, but are not included in the secondary efficacy analysis, due to their legal status. Response profiles for each arm are based on each participant’s individual rates of weekly abstinence data, including negative oral fluid results and daily self-reports of non-opioid drug use/non-use (TLFB).

The secondary safety endpoint is the prevalence of all adverse events (AEs), serious adverse events (SAEs), adverse device effects (ADEs), serious adverse device effects (SADEs), unanticipated adverse device effects (UADEs), and device deficiencies.

Supportive and exploratory measures. Treatment retention will be measured throughout the inpatient and outpatient phases. Self-stimulation intensity (in 5-min bins), duration, and device on/off data from each NET Device are automatically transmitted to a computer server and processed offline. Opioid withdrawal symptoms, craving severity, and positive/negative affect are measured daily during the first inpatient week. Measures of depression, anxiety and stress, sleepiness, and health-related quality of life are obtained at the conclusion of inpatient and outpatient phases.

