## ***Statistical analysis plan***

Sample size determination. Sample size is based on statistical power analyses for the primary hypothesis based on single primary outcome (opioid abstinence without MOUD). A conservative approach was used to preserve power with a smaller effect size than observed from prior uncontrolled, non-blinded intervention studies with the NET Device. Power analyses examined sample sizes required to detect clinically meaningful group differences between sham and active groups. This represents standardized difference between the two groups after adjusting for the effect of the covariate “duration of inpatient residence” (which is capped at 28 days). Sample size determination was carried out *via* simulation in R-software; 5000 iterations were run in which group means were generated using a mixed-effect additive model. Sample size is a function of hypothesized effect size (standardized group difference) and the sign and magnitude of the regression coefficient (duration of inpatient residence). With projected N=100 (enrolled) there will be sufficient power to detect a standardized effect size of 0.45 or higher.

Missing data. In this ITT design, a participant is “included” (becomes part of the evaluable ITT data set) when he/she completes 1-hr of device use. We expect only 5% attrition, i.e. for 100 participants who complete 1-hr of device use, we expect to consent 105 individuals. A comparable trial of a

percutaneous electrical stimulation device for treating opioid withdrawal symptoms found that 71 of 73 enrolled participants completed 1-hr of device use, only 2.8% attrition [18]. **Table 1** explains how missing data are handled, i.e. for the primary efficacy endpoint, missing data are imputed as “not opioid abstinent without MOUD”. The definition of the primary endpoint (“opioid abstinence without MOUD”) and secondary endpoint (“non-opioid abstinence”) thus covers any intermittent missing values and loss to follow-up, and is not expected to impact power of the primary analysis. Premature study termination (e.g., death, relocation, or adverse events) may result in missing data, although this attrition is expected to be low. The projected sample size (N=125) was increased to cover unforeseen events.

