Secondary endpoint analyses are not powered, but may be used to demonstrate additional benefits of the treatment, provided it has been demonstrated that the primary endpoint shows clear statistical significance, as well as clinical meaningful benefits of the treatment [19]. Analysis of the secondary endpoint resembles primary endpoint analysis, using mixed-effect model testing for the between-group main effect.

Given that participants can control the level of device stimulation, exploratory regression analyses will seek to identify potential relationships between device utilization (e.g. number of minutes device ‘on’ [non-zero intensity], average intensity while device ‘on’) and efficacy endpoints.

Expected outcomes. We selected a single primary outcome (abstinence without MOUD). From our past experience at this same treatment facility, the expected group means for sham and NET arms are 0.48 and 3.97 weeks of average opioid abstinence with standard deviations 1.19 and 3.46, respectively. This results in effect size of 1.12. This effect size based on pilot data is rather large,

which is often the case due to limited scope of the pilot study. Thus, we took a conservative approach as suggested by Kraemer et al. [20] with moderate effect size of 0.45.

Safety endpoints. Secondary safety endpoints (AEs, SAEs, ADEs, SADEs, UADEs and device deficiencies) will be summarized using descriptive statistics.

Subgroup analysis. The analysis will stratify by sex (male/female) and non-opioid SUD (presence/absence). The expected outcome is that allocation on those variables will be balanced between the two groups. It is not anticipated that the primary outcome (opioid abstinence without MOUD) will differ across these subgroups. If significant baseline group imbalance is detected on any variable and its correlation with outcome ( $\geq 0.30$ ), that variable will be included as a covariate in the inferential analyses. If systematic variation is noted by any subgroups for primary or secondary outcomes, further exploration will be conducted via cluster analysis.

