h = illicit opioid (e.g., heroin) drug screen or self-report is positivem = medication for opioid use disorder (MOUD) or self-report is positive

'-' = missing value

Cases measuring “abstinence without MOUD”:

Heroin use, no MOUD {1,1,1,h,h,1,1,1,1,1,h} = 9/12

Heroin use, no MOUD, missing weeks {1,1,1,h,h,1,--,1,1,--,} = 6/12

MOUD use, no Heroin {1,1,m,m,m,m,1,1,1,1,1} = 8/12

MOUD use, no Heroin, missing weeks {1,1,m,m,m,m,1,1,--,} = 4/12

[figure not shown]
Heroin use, MOUD use {1,1,h,h,h+m,m,m,m,m,h,1,1} = 4/12

Heroin use, MOUD use, missing weeks {1,1,h,h,h+m,m,--,m,h,--,} = 2/12

[figure not shown]
**Table 2.** Participant selection criteria

Inclusion Criteria	Exclusion Criteria

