**Figure 3. Schedule of Activities**

Schedule of Activities (SoA)	Pre-Screening	Screening	Inpatient					Outpatient	
			Week -1	Week 1			Weeks 2-3	Week 4	Weeks 5-15 Week 16
Inpatient Study Day(s)		Day 1	Day 1, Baseline	Day 1, One Hour Elapsed	Days 2-7	Day 14 Day 21	Day 28 (Discharge from Site)		
Outpatient Test Weeks								OP Wk 1-11 each Day 7	OP Wk 12 Day 7
Study Site Admission		X							
Study Site Discharge							X		
End of Study									X
Informed Consent	X	X 							
Demographics		X							
Medical and Psychiatric History		MIA 							
Drug Use History		MIA 							
Physical Exam (including height and weight)		MIA 							
Vital Signs (BP, HR, RR, O2)		MIA 							
Drug Screen		MIA 					X	X	X
Contraception, Pregnancy Test, Menstrual Cycle	X						X	X	X
Drug Use Timeline Followback Interview (TLFB)								X	X
Eligibility (Inclusion/Exclusion)	X								
Contact Data	X						X		
Randomization and Stratification	X								
COWS			X 	X	X				
Administer Active/Sham Treatment (self-administration [sa])			X	sa	sa				
Opioid Craving Scale (OCS)			X	X	X	X	X	X	X
Treatment Perception (while device in use [sa])				X	sa				
Device Satisfaction Scale (while device in use [sa])				X	sa				
Device Tolerability (while device in use [sa])				X	sa				
Dass21: Depression, Anxiety and Stress			X				X		X
PANAS-SF: Positive and Negative Affect Scale (Short Form)			X	X	X				
Epworth Sleepiness Scale			X				X		X
Concomitant Medications				X	X	X	X	X	X
Adverse Events			X	X	X	X	X	X	X
Device Deficiencies				X	sa				
SF-12 Health Related Quality of Life (Short Form)							X		X

This drug screen is wider ranging to collect stratification information

Must be >13 for inclusion on Day 1

Paper (non-electronic) source data

"MIA" is Study Site Medical Intake Assessment

Notes: "OP", outpatient. "Wk", week. "sa", self-administered. "BP", blood pressure. "COWS", Clinical Opiate Withdrawal Scale, "HR", heart rate. "RR", respiration rate. "O2", oxygen saturation.

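### Safety is a crude prevalence, but outpatient events are collected mainly at weekly calls that can be missed or stop early, so an arm with poorer attendance can look safer than it is

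*Combined protocol and SAP*

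**What the plan says.** Outcome measures defines the endpoint: "The secondary safety endpoint is the prevalence of all adverse events (AEs), serious adverse events (SAEs", followed by the device-effect categories and device deficiencies. Under Safety endpoints, the Statistical analysis plan says only that these "will be summarized using descriptive statistics". Populations for analysis puts every randomized participant in the safety dataset.

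For the outpatient phase the source is interview: "During the 12-week outpatient period, participants will be interviewed for safety and efficacy endpoints and undergo a remote drug screen". The rhythm is weekly: "Each week, the research assistant hosts a live video call with the participant". In the Schedule of Activities (Figure 3), the row "Adverse Events" is marked from Day 1 baseline through the inpatient visits and then at outpatient weeks 1–11 and 12. Device deficiencies are marked only while the device is in use, which is at most 7 days.

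Missed weeks are foreseen. Table 1 works three cases of this kind, one labelled "Heroin use, no MOUD, missing weeks". The Missing data paragraph handles them for efficacy: "for the primary efficacy endpoint, missing data are imputed as" not abstinent. It says the primary and secondary efficacy definitions thereby cover missing values. It gives no rule for safety. Lost to follow-up means missing every post-discharge call, so a participant who attends 1 of 12 calls is not classed as lost.

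**The concern.** A percentage with everyone randomized in the denominator needs equal observation before it can be compared between arms. Here observation after discharge depends on whether the participant takes the call. A missed week counts as a failure for efficacy, but with no rule for safety it simply adds no event. If one arm attends less, fewer of its outpatient events reach the table, while its denominator stays the same.

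The outpatient part of the safety table deserves this care. Participants are warned about overdose risk after loss of tolerance, and the trial has no data safety monitoring board, so this descriptive table carries much of the safety comparison. The 5% attrition in the sample size section gives no reassurance, because it concerns completion of the first hour of device use and not later calls.

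**Working it through.** The documents state no event rate, no call attendance and no expected safety result, so there is no figure to reproduce. What follows is illustration.

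**From the documents:** 12 outpatient weeks, one call a week, 50 per arm. **Assumed:** the same true event risk in both arms, with the weekly risks and attendance levels given below.

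**1. Contact stops early.** With weekly hazard h and contact for w weeks, the recorded proportion with an event is 1 − exp(−h·w). No later call exists to recover what follows.

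| h per week | weeks observed | recorded |
|---|---|---|
| 0.05 | 6.0 vs 8.4 | 25.9% vs 34.3% |
| 0.02 | 6.0 vs 8.4 | 11.3% vs 15.5% |
| 0.05 | 5 vs 8 | 22.1% vs 33.0% |

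**2. Calls missed now and then, missed events never recovered.** Let p be the true 12-week risk and v = 1 − (1 − p)^(1/12) the weekly risk. With attendance a, the recorded proportion is 1 − (1 − v·a)^12. At p = 40%, v = 0.0417.

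| p in both arms | attendance | recorded |
|---|---|---|
| 20% | 90% vs 70% | 18.2% vs 14.4% |
| 40% | 90% vs 90% | 36.8% vs 36.8% |
| 40% | 90% vs 80% | 36.8% vs 33.4% |
| 40% | 90% vs 70% | 36.8% vs 29.9% |
| 40% | 90% vs 50% | 36.8% vs 22.3% |
| 60% | 90% vs 70% | 56.0% vs 47.0% |

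**3. Calls missed now and then, but the next attended call recovers the events.** Only weeks after the last attended call are lost. If L is the last attended week, P(L) = a(1 − a)^(12 − L) for L = 1 to 12, L = 0 has probability (1 − a)^12, and the recorded proportion is 1 − E[(1 − v)^L]. At p = 40% this gives 39.7% vs 38.9% (attendance 90% vs 70%) and 39.7% vs 37.3% (90% vs 50%). Recall nearly removes the gap here, but it cannot help in case 1.

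**4. Adding the inpatient period.** With a fully observed inpatient prevalence of 50% (assumed), the 36.8% vs 29.9% case becomes 1 − 0.5 × 0.632 = 68.4% vs 1 − 0.5 × 0.701 = 65.0%. A combined figure roughly halves the visible gap, because inpatient events dilute it.

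**5. Which person-time to use.** Take h = 0.05, attendance 90% vs 70%, and recall at the next call. Mean weeks covered (E[L]) are 11.89 vs 11.57; mean weeks attended are 12 × 0.9 = 10.8 vs 12 × 0.7 = 8.4. Expected recorded events per person are 0.05 × 11.89 = 0.594 vs 0.05 × 11.57 = 0.579.

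- Per attended week: 0.594/10.8 = 0.055 vs 0.579/8.4 = 0.069, a false 25% excess in the poorer-attending arm.
- Per covered week: 0.594/11.89 = 0.050 vs 0.579/11.57 = 0.050.

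The denominator must therefore match the recall window.

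**6. When true risks differ.** With true 12-week risks of 40% vs 55%, attendance 90% vs 70% and no recall, the recorded values are 36.8% vs 42.5%. The poorer-attending arm still looks worse, but its excess falls from 15 points to 5.7. In this setting it looks safer only if its weekly risk is below about 0.9/0.7 = 1.29 times that of the other arm.

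**The case against.** A reader might infer that the poorer-attending arm will look safer. The documents do not support that certainty. They give no attendance by arm, and equal attendance produces no gap. They do not say that calls are the only source of events. The 7-day look-back is written for the drug-use review and not for adverse events, so a later call could recover missed ones. Step 6 shows that a large enough true excess would still be visible.

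A reader might also infer that the primary hypothesis implies unequal attendance. It concerns abstinence without MOUD and says nothing about who takes calls. Nor does any text require the inpatient and outpatient periods to be pooled. A descriptive summary leaves room for tables by period, and device effects are already listed as their own categories.

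Further, safety is not tested. With 50 per arm, the standard error of a 26% vs 34% contrast is √(0.259 × 0.741/50 + 0.343 × 0.657/50) ≈ 9 points, so the illustrated bias is under one standard error. Retention is also to be measured in both phases, so a reader could be shown it.

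All of this limits the size and certainty of the point. What stands is that the plan names no denominator of observed time, no recall period for adverse events and no rule for missed safety weeks, and does not link retention to the safety table. Recall at the next call also does nothing for participants whose contact ends early. A bias smaller than the sampling error is still a bias in a known direction, and it can be made visible with data already collected.

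**Conclusion.** The point holds in conditional form. If attendance differs by arm, outpatient AEs and SAEs in the poorer-attending arm will tend to be under-counted, and the crude prevalence can make that arm look safer than it is. The size is unknown. Under the assumptions shown, with equal true risk, outpatient gaps run from under 1 point (occasional misses with recall at the next call) through about 7 to 8 points (90% vs 70% attendance without recall at 40% true risk, or contact ending at 6.0 vs 8.4 weeks) to about 15 points (90% vs 50% without recall at 40% true risk). Events during the inpatient stay and device use do not depend on the calls and are largely unaffected. The efficacy analysis is not touched. This is a cheap improvement to a descriptive table and worth making before the data are analysed.

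**What to change.** 1. Present safety separately for the device/inpatient period and the outpatient period.
2. At each attended call, ask about adverse events since the last completed contact, and write that recall period into the plan.
3. For the outpatient period, give by arm the number and percentage of participants with an event and, beside it, events per observed person-week with a 95% CI. Count time at risk as the weeks covered by completed interviews including their recall window, that is, from discharge to the last completed contact. Do not use attended weeks alone, for the reason in step 5.
4. Show attended calls and observed weeks by arm in the same table, including how many participants had no completed outpatient contact. They stay in the percentage but contribute no person-time.

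The cost is some SAP wording, one extra column and a longer recall period at calls that follow a gap. If the longer recall cannot be introduced for calls already made, say which rule applied to them. Person-time does not remove bias when contact is lost because of an event, such as relapse, overdose or death, and the report should say so.

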### ***Participant selection criteria***

Screening includes informed consent, HIPAA authorization, assessment of demographics, contact data, pregnancy testing, contraception methods, medical history, and urine drug testing (including fentanyl, buprenorphine, and methadone). Assessments are aligned with the treatment

facility's standard of care such that electronic case report forms (eCRFs) can be rapidly reviewed for study eligibility by the remote investigator, given the time-sensitive nature of enrollment.

During the recruitment and informed consent process, participants are repeatedly told they can receive FDA-approved MOUD at the treatment facility instead of participating in the study. They are also told that upon discontinuation of device stimulation, and/or if they drop out of the study, they can receive TAU (including MOUD) at any time. All participants are given a "loss-of-opioid tolerance" warning (i.e. stopping opioids leads to reduced tolerance, and subsequent opioid use increases their risk of overdose and death), which they must sign. Participants are also given a naloxone kit upon discharge from the treatment facility and educated on its use. All of these procedures are documented in the medical record and case report forms.

**Table 2** presents study inclusion and exclusion criteria. For inclusion, participants ages 18-65 years old must have current OUD, present in otherwise good health, be seeking opioid discontinuation at the treatment facility, self-report that they wish to become/remain abstinent without using MOUD, be willing to follow study procedures, provide informed consent and use medically-accepted highly effective contraception. An additional criterion (following informed consent) is that device use will not begin until the Clinical Opiate Withdrawal Scale (COWS [17]) total score is 13 or greater (at least moderate withdrawal); thus, a consented participant could be dis-enrolled if the latter criterion is not met. Exclusion criteria include pregnancy or lactation, serious current psychiatric disorder (schizophrenia, bipolar) or use of neuropsychiatric medications that may overlap with NET's proposed mechanisms of action (e.g. anxiolytics, antidepressants, anticonvulsants, sedating H1-receptor antihistamines, prescription or over-the-counter stimulants), need for detoxification from alcohol or benzodiazepines, past 300-day exposure to extended-release buprenorphine, certain chronic illnesses (especially seizures), unstable medical conditions, or presence of cardiac pacemaker.

## ***Data & safety monitoring***

Oversight of data management and quality assurance is the responsibility of the investigator with input from the Study Monitor designated by the sponsor. Trial data are managed with a sponsor-designed electronic source data system. This system provides source data capture, modification, correction and access based on pre-defined roles, e.g. only the investigator can determine inclusion/exclusion. Specific eCRF data are exported to a FDA-compliant electronic data capture (Advarra) system at Wayne State University, where the biostatistical team manages and analyzes outcome measures. There is no data safety monitoring board for this trial.

